4. ANALYSIS SETS (POPULATIONS FOR ANALYSIS)

Data for all participants will be assessed to determine if participants meet the criteria for inclusion in each analysis population prior to unblinding and releasing the database and classifications will be documented per standard operating procedures.

The study part referred to below can be either **PART-1: SAD**, **PART-2: MAD**, **PART-3: Relative Bioavailability/Food Effect cohort**, **PART-4: Metabolism and Excretion cohort**, or **PART-5: Supratherapeutic Exposure cohort**, unless otherwise specified.

Population	Description
Enrolled/Randomly assigned to study intervention	"Enrolled" means a participant's agreement to participate in a clinical study following completion of the informed consent process. Potential participants who are screened for the purpose of determining eligibility for the study, but do not participate in the study, are not considered enrolled, unless otherwise specified by the protocol.
Evaluable	All participants randomly assigned to study intervention and who take at least 1 dose of study intervention for the given part of the study.
Safety	All participants randomly assigned to study intervention and who take at least 1 dose of study intervention. Participants will be analyzed according to the product they actually received.
PK Concentration Set	All participants randomly assigned to study intervention and who take at least 1 dose of study intervention and in whom at least 1 concentration value is reported for the given part of the study.
PK Parameter Set	All participants randomly assigned to study intervention and who take at least 1 dose of study intervention and in whom at least 1 of the PK parameters of interest are reported for the given part of the study.

Population	Description
Excretion Analysis Set	In PART-4, excretion analysis population will be defined by evaluable participants who have received 1 dose of PF-07321332 and who have completed drug related material concentration (urinary and fecal) data and who had no protocol deviations that may have affected the mass balance analysis.

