## Data Monitoring Committee or Other Independent Oversight Committee: No

#### **Statistical Methods**

The sample size for PART-1 and PART-2 of the study has been chosen based on the need to minimize exposure of healthy participants to a new chemical entity and the requirements to provide adequate safety and toleration and PK information at each dose level.

For PART-3, the sample size will provide adequate precision to compare the relative bioavailability of a tablet formulation of PF-07321332 relative to oral suspension.

For Part 4: A sample size of approximately 6 male participants (with at least 4 completers) is chosen based on the industry standard sample size for metabolism and excretion studies. This sample size was not justified by any empirical data or hypothesis testing criteria.

[figure not shown]
For Part 5: A sample size of up to 12 participants (with at least 10 completers) is chosen based on the need to provide adequate safety, tolerability and PK information at each dose level and/or administration schedule.

The data from the 5 parts of this study will be analyzed and reported separately in a single CSR.

All safety analyses will be performed on the safety analysis set, which is defined as all participants randomly assigned to study intervention and who receive at least one dose of study intervention. Participants will be analyzed according to the product they actually received. Safety data will be presented in tabular and/or graphical format and summarized descriptively, where appropriate. Plasma concentrations will be listed and summarized descriptively by PK sampling time and treatment. The plasma PK parameters will be summarized descriptively by dose. No formal inferential statistics will be applied to the PK data apart from the comparisons of formulation and food effect in either PART-1 or PART-3, if conducted.

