## PART-4: Metabolism and Excretion

This part is an open-label, non-randomized, single period cohort to evaluate the metabolism and excretion of PF-07321332 in healthy male participants. Only males will be included in this study given the desire to enroll a homogeneous population due to the small sample size.

A single dose of PF-07321332 is considered appropriate as available data do not indicate PF-07321332 PK are time-dependent, and hence, single dose data are considered predictive of steady state.

The urine and feces samples collected will only be analyzed at the end of the study to determine the amount of drug related material excreted. Considering the half-life and variability in gastrointestinal transit time, feces and urine will be collected up to 10 days after dosing to allow near complete collection of the drug or drug related materials.

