#### 5.4. Screen Failures

Screen failures are defined as participants who consent to participate in the clinical study but are not subsequently randomly assigned to study intervention/enrolled in the study. Screen failure data are collected and remain as source and are not reported to the clinical database.

Individuals who do not meet the criteria for participation in this study (screen failure) may be rescreened.

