2. INTRODUCTION

The current study is the first clinical administration with PF-07321332. It is a 5-part study combining **PART-1: SAD**, **PART-2: MAD**, **PART-3: relative bioavailability/food effect**, **PART-4: metabolism and excretion** and **PART-5 supratherapeutic exposure (SE)**. PART-1 and 2 are randomized, double-blind, sponsor-open, placebo-controlled trial to evaluate safety, tolerability and PK of single and multiple escalating oral doses of PF-07321332 in

*healthy adult participants and **PART-3** is a randomized open label study to evaluate relative bioavailability and food effect of an oral tablet formulation. **PART-2** of the study may also evaluate the safety tolerability and PK in Japanese participants. **PART-4** is an open-label, non-randomized, single period to evaluate the metabolism and excretion of PF-07321332. **PART-5** is a double-blind, sponsor-open, randomized, cross-over study to evaluate safety and tolerability at supratherapeutic exposures.*

This statistical analysis plan (SAP) provides the detailed methodology for summary and statistical analyses of the data collected in Study C4671001. This document may modify the plans outlined in the protocol; however, any major modifications of the primary endpoint definition or its analysis will also be reflected in a protocol amendment.

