6.2. Secondary Endpoint(s)

The secondary endpoints in **PART-1**, **PART-2**, **PART-4** and **PART-5**, as well as the primary endpoints in **PART-3**, are related to PK and are described herein.

No formal inferential statistics will be applied to the plasma PK data apart from the comparisons of formulation and food effect in either **PART-1** or **PART-3**

The PK parameters detailed in [Section 3.3.1](#) will be listed and summarized for participants in the PK Parameter Set (as defined in [Section 4](#)). Missing values will be handled as detailed in [Section 5.3](#). Each PK parameter will be summarized by matrix (plasma or urine), treatment and dose. Each summary will include the set of summary statistics as specified in

Table 4. Summaries will be performed separately for PART-1, PART-2, PART-3, PART-4 and PART-5.

Table 4. PK Parameters to be Summarized Descriptively

Parameter	Summary Statistics
AUC _{last} , AUC _{inf} , C _{max} , CL/F, V _z /F, AUC _{last(dn)} , AUC _{inf(dn)} , C _{max(dn)} , AUC _τ , C _{min} , C _{av} , R _{ac} , R _{ac,Cmax} , PTR, AUC _{τ(dn)} , A _τ , A _τ %, and CL _r	N, arithmetic mean, median, cv%, standard deviation, minimum, maximum, geometric mean and geometric cv%.
T _{max}	N, median, minimum, maximum.
t _{1/2}	N, arithmetic mean, median, standard deviation, minimum, maximum.

To assess the relationship between the PK parameters and dose, dose normalized C_{max}, AUC_{last}, and AUC_{inf} (**PART-1**) and C_{max} and AUC_τ (**PART-2**) of PF-07321332 will be plotted against dose (using a logarithmic scale), and will include individual participant values and the geometric means for each dose. Geometric means will have a different symbol than the individual values. In Part-2, the data from the Japanese subjects will be identified by different symbols/colours. The values will be dose normalized (to a 1 mg dose) by dividing the individual values and raw geometric means by dose. A footnote will be added to the plots to indicate that geometric means are presented. All dose normalized parameters will be listed along with other individual PK parameters.

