6.6. Safety Summaries and Analyses

In all 5 parts of the study, all safety analyses will be performed on the Safety Analysis Set.

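### Do the analysis-set definitions shut out the participants of PART-4, which is not randomized?

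*SAP*

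**What the plan says.** SAP section 4 and Protocol 9.3 use the same text for four sets. The Evaluable set is "All participants randomly assigned to study intervention and who take at least 1 dose of study intervention for the given part of the study". The Safety, PK Concentration and PK Parameter sets open with the same requirement of random assignment and at least one dose, and the two PK sets add a condition that data exist. The Protocol synopsis, under Statistical Methods, repeats the requirement for safety: that set is "defined as all participants randomly assigned to study intervention and who receive at least one dose of study intervention".

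PART-4 does not fit that wording. Protocol 4.2 states: "This part is an open-label, non-randomized, single period cohort to evaluate the metabolism and excretion of PF-07321332 in healthy male participants". SAP section 2 describes it in the same way, as "non-randomized, single period to evaluate the metabolism and excretion of PF-07321332".

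The fifth set, for excretion, exists only for PART-4. Its text reads: "excretion analysis population will be defined by evaluable participants who have received 1 dose of PF-07321332".

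On use, SAP 6.6 states: "In all 5 parts of the study, all safety analyses will be performed on the Safety Analysis Set". SAP 6.2 takes the PK parameters from the PK Parameter Set and adds: "Summaries will be performed separately for PART-1, PART-2, PART-3, PART-4 and PART-5".

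**The concern.** An analysis set is a membership rule, and SAP section 4 makes membership a formal step, to be decided and documented before the database is unblinded and released. If the rule asks for random assignment and a whole study part has none, that part fails the rule. SAP section 4 lists PART-4 among the parts its definitions cover and gives it no exception.

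At stake on that reading would be all PART-4 safety summaries and all PART-4 plasma PK, both of which are secondary endpoints. The Excretion Analysis Set might be affected too, since it is built on evaluable participants. The same looseness appears in Protocol 1.1, Protocol 9.2 and SAP 2.2.7, which count the 6 PART-4 places within a total described as randomized.

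**Working it through.** **Headcount.** The inputs are the part sizes in Protocol 9.2 and SAP 2.2.7: PART-1 12, PART-2 up to 30 (5 cohorts of 6), PART-3 up to 18, PART-4 6, PART-5 up to 12.

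- Stated total: 12 + 30 + 18 + 6 + 12 = 78. This reproduces the plan's figure.
- Places in randomized parts: 78 − 6 = 72.
- PART-4 share: 6 / 78 = 0.077, or 7.7%.

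The total of 78 is right as a count of planned places. Only the word randomized does not suit 6 of them.

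**Membership of PART-4 under two readings.**

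| Set | Word for word | As the rest of the plan uses it |
|---|---|---|
| Evaluable | 0 of about 6 | all who were dosed |
| Safety | 0 of about 6 | all who were dosed (SAP 6.6) |
| PK Concentration | 0 of about 6 | dosed, with at least one concentration (SAP 6.2) |
| PK Parameter | 0 of about 6 | dosed, with at least one parameter (SAP 6.2) |
| Excretion | 0 of about 6, by inference | dosed, complete urine and fecal data, no relevant deviation |

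**Which reading the plan supports.** These places only make sense if PART-4 participants belong to the sets:

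1. SAP section 4 names PART-4 as a part to which the definitions refer.
2. SAP 6.6 and Protocol 9.4.5.1 put the safety analyses of all five parts on the Safety Analysis Set.
3. SAP 6.2 summarizes PART-4 PK on the PK Parameter Set. SAP Table 2 has PART-4 in its title, and its footnotes remove only the dose-normalized parameters for that part, so the others are meant to be reported.
4. SAP 3.5.2 to 3.5.4 define a PART-4 baseline for laboratory data, vital signs and ECG.
5. SAP 6.5.2 includes PART-4 in the demographic summaries.

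**The Excretion set.** Its dependence on the random-assignment condition is an inference from the word evaluable. A definition that can hold only PART-4 participants is not sensibly read as one that holds nobody. SAP 6.1 names no analysis set for the PART-4 primary recovery endpoint and says that it will be calculated and reported separately, so the definitions give no ground for saying that this endpoint is lost.

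**What random assignment does in these definitions.** PART-4 is one cohort in which everyone is planned to receive the same regimen. There is no comparison between randomized groups to protect, and no one can be analysed in the wrong arm. The working condition for PART-4 is having taken a dose. Dropping or rewording the randomization clause gives the same members as the second column above.

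**The case for a change.** The best argument for a change is that a written rule should be right without appeal to intent. SAP version 2.0 was revised to bring in PART-4 and gained a new set for it, yet the four general definitions make no allowance for a part without randomization, which looks like a missed update. Better wording was at hand: Protocol 5.4 defines screen failures with the pair "randomly assigned to study intervention/enrolled in the study", and the set definitions keep only its first half. Nor does other text rescue the wording. The row headed with both enrolment and random assignment goes on to define only enrolment. Protocol 6.3.1 speaks of a randomization schedule and exempts PART-3 and PART-4 from blinding only, but that does not make PART-4 randomized.

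All of that stands as a description of the text. What does not stand is the step from loose wording to a risk for the analysis. The paired wording in Protocol 5.4, the row label and the count of 78 point to one habit: the documents use random assignment loosely for entry into the study. Someone classifying participants before release would have to overlook SAP 6.2 and 6.6, and the scope sentence in SAP section 4 itself, to leave PART-4 out. Correcting every place would also mean editing the Protocol synopsis, 9.2 and 9.3 by amendment, which under Protocol 10.1.1 goes to the IRB/EC. That is more than a clerical slip justifies.

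**Conclusion.** The inconsistency is genuine and clerical. Four definitions and one synopsis sentence ask for random assignment that PART-4 does not have, and three count sentences describe 78 places as randomized when 72 are. The participants concerned number about 6, or 7.7% of planned places. The expected effect on results is nil: every dosed PART-4 participant would be analysed for safety, and PK and excretion membership would turn on the data conditions already written into those sets. No inferential comparison, sample size or endpoint definition depends on the phrase.

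This rests on two assumptions: that analysts follow SAP 6.2 and 6.6, which cover PART-4, over a literal reading of a shared definition, and that PART-4 enrols about the 6 planned. No change to the plan follows.

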5. GENERAL METHODOLOGY AND CONVENTIONS

5.1. Hypotheses and Decision Rules

There is no statistical hypothesis testing planned for this study and no statistical decision rules will be applied.

5.2. General Methods

Unless otherwise stated, all summaries and plots will be presented by treatment.

5.2.1. Analyses for Continuous Endpoints

Continuous variables will be presented using summary statistics: number of observations, arithmetic mean, standard deviation, cv%, median, minimum and maximum values.

Log transformed continuous variables will be presented using summary statistics: number of observations, arithmetic mean, median, cv%, standard deviation, minimum, maximum, geometric mean and geometric cv%.

5.2.2. Analyses for Categorical Endpoints

Categorical variables will be presented using summary statistics: number of observations and percentages.

5.3. Methods to Manage Missing Data

For the analysis of safety endpoints, the sponsor data standard rules for imputation will be applied.

In all PK data presentations (except listings), concentrations below the limit of quantification (BLQ) will be set to zero.

In listings, BLQ values will be reported as “<LLQ”, where LLQ will be replaced with the value for the lower limit of quantification (LLQ).

For PK summary tables and plots of mean/median profiles, statistics will be calculated having set concentrations to missing if 1 of the following cases is true:

1. A concentration has been collected as ND (ie not done) or NS (ie no sample),
2. A deviation in sampling time is of sufficient concern or a concentration has been flagged anomalous by the pharmacokineticist/statistician.

If a PK parameter cannot be derived from a participant's concentration data, the parameter will be coded as NC (ie not calculated). (Note that NC values will not be generated beyond the day that a participant discontinues). In summary tables, statistics will be calculated by setting NC values to missing; and statistics will be presented for a particular dose with ≥ 3 evaluable measurements.

If an individual participant has a known biased estimate of a PK parameter (due for example to an unexpected event such as vomiting before all the compound is adequately absorbed in the body), this will be footnoted in summary tables and will not be included in the calculation of summary statistics or statistical analyses.

6. ANALYSES AND SUMMARIES

Separate tables will be produced for **PART-1: SAD**, **PART-2: MAD**, **PART-3: Relative Bioavailability/Food Effect Cohort**, **PART-4: Metabolism and Excretion Cohort** and **PART-5: Supratherapeutic Exposure Cohort**, unless otherwise specified. Placebo and Placebo + Ritonavir will be separate treatment groups. In Part-2, Japanese and non-Japanese will be separate treatment groups.

6.1. Primary Endpoint(s)

The primary endpoints in PART-1, PART-2 and PART-5 are related to safety/tolerability and their analyses are described Section 6.6.

The primary endpoints in PART-3 are the plasma PK endpoints whose analyses are described in Section 6.2.

The primary endpoints in PART-4 are percent recovery and cumulative recovery of drug-related material in urine, feces based on total administered dose. This will be calculated and reported separately.

6.2. Secondary Endpoint(s)

The secondary endpoints in **PART-1**, **PART-2**, **PART-4** and **PART-5**, as well as the primary endpoints in **PART-3**, are related to PK and are described herein.

No formal inferential statistics will be applied to the plasma PK data apart from the comparisons of formulation and food effect in either **PART-1** or **PART-3**

The PK parameters detailed in [Section 3.3.1](#) will be listed and summarized for participants in the PK Parameter Set (as defined in [Section 4](#)). Missing values will be handled as detailed in [Section 5.3](#). Each PK parameter will be summarized by matrix (plasma or urine), treatment and dose. Each summary will include the set of summary statistics as specified in

Table 4. Summaries will be performed separately for PART-1, PART-2, PART-3, PART-4 and PART-5.

Table 4. PK Parameters to be Summarized Descriptively

Parameter	Summary Statistics
AUC _{last} , AUC _{inf} , C _{max} , CL/F, V _z /F, AUC _{last(dn)} , AUC _{inf(dn)} , C _{max(dn)} , AUC _τ , C _{min} , C _{av} , R _{ac} , R _{ac,Cmax} , PTR, AUC _{τ(dn)} , A _τ , A _τ %, and CL _r	N, arithmetic mean, median, cv%, standard deviation, minimum, maximum, geometric mean and geometric cv%.
T _{max}	N, median, minimum, maximum.
t _{1/2}	N, arithmetic mean, median, standard deviation, minimum, maximum.

To assess the relationship between the PK parameters and dose, dose normalized C_{max}, AUC_{last}, and AUC_{inf} (**PART-1**) and C_{max} and AUC_τ (**PART-2**) of PF-07321332 will be plotted against dose (using a logarithmic scale), and will include individual participant values and the geometric means for each dose. Geometric means will have a different symbol than the individual values. In Part-2, the data from the Japanese subjects will be identified by different symbols/colours. The values will be dose normalized (to a 1 mg dose) by dividing the individual values and raw geometric means by dose. A footnote will be added to the plots to indicate that geometric means are presented. All dose normalized parameters will be listed along with other individual PK parameters.

Supporting data from the estimation of t_{1/2} will be listed by treatment and dose where applicable: terminal phase rate constant (k_{el}); goodness of fit statistic from the log-linear regression (r²); the percent of AUC_{inf} based on extrapolation (AUC_{extrap} %); and the first, last, and number of time points used in the estimation of k_{el}. These data may be included in the CSR.

Presentations for PF-07321332 concentrations will be presented using participants in the PK Concentration Set (as defined in [Section 4](#)) and will include:

- a listing of all concentrations sorted by participant ID, dose, matrix and nominal time post-dose. The concentration listing will also include the actual times. Deviations from the nominal time will be given in a separate listing.
- a summary of concentrations by dose and nominal time post-dose, where the set of statistics will include n, mean, median, standard deviation, coefficient of variation (cv),

minimum, maximum and the number of concentrations above the lower limit of quantification.

- individual concentration-time plots by dose (on both linear and semi-log scales) against actual time post-dose (there will be separate spaghetti plots for each dose per scale).
- individual concentration-time plots by participant (on both linear and semi-log scales) against actual time post-dose (there will be separate spaghetti plots for each dose per scale).
- median concentration-time plots (on both linear and semi-log scales) against nominal time post-dose by dose (all doses on the same plot per scale, based on the summary of concentrations by dose and time post-dose).
- mean concentration-time plots (on both linear and semi-log scales) against nominal time post-dose by dose (all doses on the same plot per scale, based on the summary of concentrations by dose and time post-dose).

The scale used for the x-axis (time) of these plots will be decided on review of the data, and will depend on how long PF-07321332 concentration is quantifiable in the matrix.

For summary statistics, median and mean plots by sampling time, the nominal PK sampling time will be used. For individual participant plots by time, the actual PK sampling time will be used.

For **PART-2**, urine amounts of PF-07321332 as listed in [Table 3](#) will be listed and summarized descriptively, if data permit.

To assess any effect of food/formulation in **PART-3**, natural log transformed AUC_{last} , C_{max} , and AUC_{inf} (if data permit) for PF-07321332 will be analyzed using a mixed effects model with sequence, period and treatment included as a fixed effect and participant nested within sequence as a random effect. If performed, to assess any effect of food/formulation in **PART-1**, natural log transformed AUC_{last} , C_{max} , and AUC_{inf} (if data permit) for PF-07321332 will be analyzed using a mixed effects model with treatment as a fixed effect and participant as a random effect using participants with data from both periods only. The Kenward-Roger adjustment for the degrees of freedom will be used. Estimates of the adjusted mean differences (Test-Reference) and corresponding 90% CIs will be obtained from the model. The adjusted mean differences and 90% CIs for these differences will be exponentiated to provide estimates of the ratio of adjusted geometric means (Test/Reference) and 90% CIs for these ratios.

[figure not shown]
The following comparisons will be made:

Comparison	Test	Reference
Formulation	PF-07321332 tablet formulation in fasted state (B)	PF-07321332 oral suspension in fasted state (A)

Food Effect	PF-07321332 tablet formulation in fed (high fat meal) state (C)	PF-07321332 tablet formulation in fasted state (B)
-------------	---	--

